4.3 Justification for Dose

Dasiglucagon bolus dose of 0.6 mg SC has been approved by FDA for the treatment of severe hypoglycemia in pediatric and adult patients with diabetes aged 6 years and above. Based on population PK model predictions and Pop PK/PD Simulations (Study 20-046), the 0.6 mg dose is expected to be an appropriate dose in an older subset of children < 6 years and ≥ 2 years,

whereas a lower dose of 0.3 mg is expected to be an appropriate dose in a younger subset of children < 6 years. The results from the present trial will be used to determine the appropriate dose(s) for children < 6 years.

The rationale for the suggested split in doses between the 2 groups, which are partially overlapping, is to maximize the efficacy benefit in this vulnerable age group without any increase in untoward effects. Young children are more susceptible to low blood glucose and in addition to this, it has been shown that the frequency of severe hypoglycemia is one of the factors that has a negative impact on specific neuropsychological functions.

4.3.1 Pharmacokinetics

In the population PK report 19-077,⁴ 2 models were developed to cover children below 6 years of age: the final population PK model and an alternative population PK model. The final model showed a piece-wise linear relationship between age and relative bioavailability. The alternative model assumed a trial effect of bioavailability for the pediatric trial ZP4207-17086 (age 6 to 17 years) versus adults but was less robust than the final model. The Pop PK/PD Simulations (Study 20-046) used the Pop PD model and both PK models.

Children < 6 years and ≥ 2 years: justification for 0.6 mg dose

The final Pop PK model (Study 19-077) showed a mean C_{max} and AUC that was 1.9 and 1.5 times higher in 2- to 3-year-olds with a 0.6 mg dose compared to the exposure in adults with 0.6 mg, respectively. The alternative model indicated these values to be 4.5 and 3.7 times higher compared to adults. The span of PK predictions based on the final and alternative PK models can be seen as a possible realistic range.

Children preferably < 4 years: justification for 0.3 mg dose

The final Pop PK model (Study 19-077) showed a mean C_{max} and AUC that was 1.4 and 1.1 times higher in 0- to 1-year-olds for a dose of 0.3 mg compared to the exposure in adults with 0.6 mg, respectively. The ratio was 0.9 and 0.7 for C_{max} and AUC in 3- to 4-year-olds for a dose of 0.3 mg compared to the exposure in adults with 0.6 mg, respectively.

The alternative model indicated these values for C_{max} and AUC to be 4.0 and 3.1 times higher in 0- to 1-year-olds and 2.0 and 1.7 times higher in 3- to 4-year-olds compared to adults. The span of PK predictions based on the final and alternative PK models can be seen as a possible realistic range.

4.3.2 Cardiac repolarization and dasiglucagon concentration

To assess the effect of dasiglucagon on cardiac repolarization, trial ZP4207-17144 was conducted in adult healthy volunteers to investigate the effect of IV dasiglucagon up to 1.5 mg on electrocardiogram (ECG) parameters. Dasiglucagon showed no clinically relevant effects on

studied ECG parameters and an effect of dasiglucagon on corrected QT prolongation exceeding 10 ms was excluded within the observed concentration range up to ~30,000 pmol/L.

Children < 6 years and ≥ 2 years: justification for 0.6 mg dose

Since the predicted C_{max} from both PK models (0.6 mg dose: final model: 1,230 to 4,240 pmol/L in children aged 2 to 3 years and alternative model: 3,090 to 10,500 pmol/L in children aged 2 to 3 years) is substantially lower (at least 2.9 times lower) than the observed concentration range, the use of 0.6 mg dasiglucagon is considered to be safe in children < 6 years and \geq 2 years with regards to the risk of QT prolongation.

Children preferably < 4 years: justification for 0.3 mg dose

Since the predicted C_{max} from both PK models (0.3 mg dose: final model: 926 to 3,660 pmol/L in children aged 0 to 1 years and alternative model: 2,600 to 10,500 pmol/L in children aged 0 to 1 years) is substantially lower (at least 2.9 times lower) than the observed concentration range, the use of 0.3 mg dasiglucagon is considered to be safewith regards to the risk of QT prolongation.

4.3.3 Safety

Overall, the safety profile for dasiglucagon, as determined from the completed development program for treatment of severe hypoglycemia in adults and pediatric patients aged ≥ 6 to ≤ 17 years with a dose of 0.6 mg, is consistent with the well-known class effects associated with glucagon receptor agonism. The most frequently reported AEs were nausea and vomiting, which are known side effects following administration of glucagon.

In the pediatric trial ZP4207-17086, a higher frequency of gastrointestinal events was seen in adolescents than in patients 7 to 11 years of age and no association between nausea/vomiting and exposure (C_{max} and AUC) was detected. In the 4 trials in the development program where a range of dasiglucagon doses was tested in adults, nausea and vomiting were primarily reported with doses of 0.3 mg or higher. The reported nausea and vomiting were mild or moderate and transient. Nausea and vomiting appeared at a similar frequency to marketed glucagon in the pivotal trials in adults. Apart from nausea and vomiting (gastrointestinal AEs), there was no apparent relationship between dasiglucagon dose and the frequency of AEs in any of the trials where a range of doses up to 2 mg SC dasiglucagon was tested.

A single serious AE (SAE) (an event of hypoglycemia in an adult, which was deemed unrelated to investigational product treatment) was reported in the completed development program, and most AEs were events of mild or moderate severity. Antibody formation was observed in less than 1% of patients exposed to dasiglucagon (4/498 patients), and no immunogenicity-related AEs were identified for any of the patients who had anti-dasiglucagon antibodies (3 adults and 1 child).

Protocol ZP4207-21052 Version 6.0, 12 Jul 2024

Taken together, rapid recovery is highly warranted in very young children due to the increased susceptibility and detrimental effects of severe hypoglycemia in this age group. Based on clinical data, no increased safety risks are expected when dosing children < 6 years and \geq 2 years with 0.6 mg dasiglucagon and children preferably below 4 years with 0.3 mg dasiglucagon even though PK simulations predict a higher exposure compared to adults and children \geq 6 years. Gastrointestinal events such as nausea and vomiting have been reported throughout the completed clinical program. In the completed pediatric trial, no relationship was seen between dasiglucagon exposure and the occurrence of nausea and vomiting that would indicate any increased risk in younger children. No effect on cardiac repolarization is expected since the maximum predicted dasiglucagon concentration in young children is substantially lower (at least 2.9 times lower) both for children < 6 years and \geq 2 years receiving 0.6 mg and children preferably below 4 years receiving 0.3 mg dasiglucagon than the dasiglucagon concentration established to have no corrected QT prolongation exceeding 10 mg in adults (trial ZP4207-17144).

4.4 End-of-Trial Definition

The end of the trial is defined as the date of the last visit of the last patient in the trial.

A patient is considered to have completed the trial if he/she has completed all phases of the trial including the last follow-up visit (Visit 3).

5 TRIAL POPULATION

Prospective approval of protocol deviations to recruitment and eligibility criteria, also known as protocol waivers or exemptions, are not permitted.

5.1 Inclusion Criteria

Children are eligible to be enrolled in the trial only if all of the following criteria apply:

Age

1. Child must be < 6 years at the time of screening.

Type of Patient and Disease Characteristics

2. Children who are confirmed as having T1D based on medical history and are receiving daily insulin therapy via insulin pump or MDI.

Informed Consent

- 3. Following receipt of verbal and written information about the trial, the parent(s) or legal guardian of the child must be capable of giving signed informed consent before any trial-related activity is carried out as described in Appendix 1 which includes compliance with the requirements and restrictions listed in the informed consent form (ICF) and in this protocol.
- 4. Ability to adhere to the protocol requirements.

Weight

5. Body weight > 8 kg.

5.2 Exclusion Criteria

Patients are excluded from the trial if any of the following criteria apply:

Medical Conditions

- 1. Known or suspected allergy to the IMP or related products
- 2. Any condition that in the investigators opinion may result in diminished hepatic glycogen stores (eg, prolonged fasting (more than 24 hours) at Visit 2
- 3. History of anaphylaxis or symptoms of severe systemic allergy (such as angioedema)
- 4. History of any hypoglycemic event indicating trial procedures to be high risk for the child, as judged by the investigator
- 5. History of severe hypoglycemic event (defined as an event associated with a seizure or loss of consciousness or requiring emergency medical personnel, a visit to the emergency department, or a hospital admission) within 3 months prior to screening
- 6. History of epilepsy or seizure disorder
- 7. Active malignancy

- Congenital heart disease
- 9. Current bleeding disorder, including anti-coagulant treatment
- 10. Known presence or history of pheochromocytoma (ie, adrenal gland tumor) or insulinoma (ie, insulin secreting pancreas tumor)
- 11. Surgery or trauma with significant blood loss within the last 2 months prior to screening

Prior/Concomitant Therapy

- 12. Use of daily systemic beta-blocker, indomethacin, warfarin, or anticholinergic drugs
- 13. Use of prescription or non-prescription medications known to cause QT prolongation

Prior/Concurrent Clinical Trial Experience

- 14. Previous participation in this trial. Participation is defined as received treatment with IMP
- 15. Receipt of any investigational drug within 3 months prior to screening

Diagnostic Assessments

- 16. Aspartate aminotransferase (AST) or alanine aminotransferase (ALT) >2.5 \times the upper limit of the normal range (ULN)
- 17. Estimated glomerular filtration rate <30 mL/min/1.73 m² according to the Modification of Diet in Renal Disease study definition
- 18. Altered electrolyte values of clinical relevance for cardiac conduction, as judged by the investigator
- 19. Clinically significant abnormal ECG at screening as judged by the investigator
- Clinically significant illness within 4 weeks before screening, as judged by the investigator

Other Exclusions

21. Any condition that might jeopardize the child's safety or compliance with the protocol as judged by the investigator

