2.1 Trial Rationale

Severe hypoglycemia is a risk in all individuals with diabetes, in particular in those requiring insulin treatment regardless of age. There is a therapeutic need for all individuals at risk for severe hypoglycemia to have access to safe and effective emergency rescue therapies should such an event occur. The present trial aims to assess the efficacy and safety of a single subcutaneous (SC) injection of dasiglucagon (0.3 mg or 0.6 mg) in children with type 1 diabetes (T1D) below 6 years of age. The trial population will include children treated with SC insulin infusion via insulin pump or multiple daily injections (MDI) in order to include children below 1 year of age. To ensure the blood volume collected in the present trial is within an acceptable percentage of total blood volume for the individual child, children must have a body weight above 8 kg (see inclusion criteria Section 5.1). Overall, the eligibility criteria allow for enrollment of a trial population closely approximating the general population of children below 6 years of age with T1D.

[figure not shown]

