10.2 Appendix 2: Clinical Laboratory Tests

Routine safety laboratory tests will be performed centrally. Samples for safety laboratory parameters will be collected at Visits 1 and 3. The following parameters will be determined:

- Clinical chemistry (measured in serum): sodium, potassium, calcium, creatinine, total bilirubin, AST, ALT. If additional clinical chemistry parameters are analyzed and reported as part of a standard chemistry panel, these data will also be evaluated.
- Hematology (measured in whole blood): hemoglobin, platelet count (thrombocytes), total
 white blood cell count (leucocytes). If additional hematology parameters are analyzed
 and reported as part of a standard hematology panel, these data will also be evaluated.
- Pharmacokinetic (PK) samples (measured in plasma): PK assessments from samples collected during Visit 2 will be analyzed by York Bioanalytical Solutions (York, United Kingdom).
- Immunogenicity: Serum samples for assessment of antibodies against dasiglucagon will be measured at screening Visit 1 and at follow-up Visit 3 by the special laboratory, York Bioanalytical Solutions (York, United Kingdom). The cell-based neutralizing antibody analyses will be performed by a special laboratory, BioAgilytix, Durham, North Carolina, USA. A description of the sample handling and sample processing, storage, and shipment at the site will be included in the laboratory manual. Immunogenicity samples are planned to be analyzed after the last patient's Visit 3.
- The clinical anti-drug antibody (ADA) assays have been validated in accordance with existing guidelines and recommendations.
- Confirmed positive anti-dasiglucagon antibody samples from treatment-induced or treatment-boosted (titer increase above 4-fold) ADA-positive patients will be assessed for binding titer, neutralizing potential and neutralizing titer as well as cross-reactivity towards endogenous glucagon. Any treatment-induced or treatment-boosted ADA-positive patients will be monitored as long as outcomes related to ADAs are detected or until the ADA level has returned to baseline.

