| 2 to < 4 years | xx (xx.x%) | xx (xx.x%) | xx (xx.x%) |
| 4 to < 6 years | xx (xx.x%) | xx (xx.x%) | xx (xx.x%) |
| Sex | | | |
| Male | xx (xx.x%) | xx (xx.x%) | xx (xx.x%) |
| Female | xx (xx.x%) | xx (xx.x%) | xx (xx.x%) |
| Unknown | xx (xx.x%) | xx (xx.x%) | xx (xx.x%) |
| Undifferentiated | xx (xx.x%) | xx (xx.x%) | xx (xx.x%) |
| Race | | | |
| American Indian or Alaska Native | xx (xx.x%) | xx (xx.x%) | xx (xx.x%) |
| Asian | xx (xx.x%) | xx (xx.x%) | xx (xx.x%) |
| Black or African American | xx (xx.x%) | xx (xx.x%) | xx (xx.x%) |
| Native Hawaiian or Other Pacific Islander | xx (xx.x%) | xx (xx.x%) | xx (xx.x%) |
| White | xx (xx.x%) | xx (xx.x%) | xx (xx.x%) |
| Not reported | xx (xx.x%) | xx (xx.x%) | xx (xx.x%) |
| Not Allowed to Ask per Local Regulation | xx (xx.x%) | xx (xx.x%) | xx (xx.x%) |
| Other | xx (xx.x%) | xx (xx.x%) | xx (xx.x%) |
| Multiple Races Checked | xx (xx.x%) | xx (xx.x%) | xx (xx.x%) |
| Ethnicity | | | |
| Hispanic or Latino | xx (xx.x%) | xx (xx.x%) | xx (xx.x%) |
| Not Hispanic or Latino | xx (xx.x%) | xx (xx.x%) | xx (xx.x%) |
| Not reported | xx (xx.x%) | xx (xx.x%) | xx (xx.x%) |
| Not Allowed to Ask per Local Regulation | xx (xx.x%) | xx (xx.x%) | xx (xx.x%) |
| Height (cm) | | | |
| n | xx | xx | xx |
| Mean (SD) | xx.x (xx.xx) | xx.x (xx.xx) | xx.x (xx.xx) |
| Median | xx.x | xx.x | xx.x |
| Min, Max | xx, xx | xx, xx | xx, xx |

| | dasiglucagon 0.3mg (N=XX) | dasiglucagon 0.6mg (N=XX) | Total (N=XX) |
|---|------------------------------|------------------------------|-----------------|
| Weight (kg) | | | |
| n | xx | xx | xx |
| Mean (SD) | xx.x (xx.xx) | xx.x (xx.xx) | xx.x (xx.xx) |
| Median | xx.x | xx.x | xx.x |
| Min, Max | xx, xx | xx, xx | xx, xx |
| Weight groups | | | |
| < 15kg | xx (xx.x%) | xx (xx.x%) | xx (xx.x%) |
| >=15kg | xx (xx.x%) | xx (xx.x%) | xx (xx.x%) |
| BMI (kg/m ²) | | | |
| n | xx | xx | xx |
| Mean (SD) | xx.x (xx.xx) | xx.x (xx.xx) | xx.x (xx.xx) |
| Median | xx.x | xx.x | xx.x |
| Min, Max | xx, xx | xx, xx | xx, xx |
| Time Since Diabetes Diagnosis ^[b] (months) | | | |
| n | xx | xx | xx |
| Mean (SD) | xx.x (xx.xx) | xx.x (xx.xx) | xx.x (xx.xx) |
| Median | xx.x | xx.x | xx.x |
| Min, Max | xx, xx | xx, xx | xx, xx |

[a] Age on consent date

[b] Date of informed consent - date of diabetes diagnosis + 1

Percentages are based on the total number of patients in the safety analysis set.

Height, weight and BMI obtained at Screening visit.

Source: xxx

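### Exclusion criterion 17 names the MDRD equation for children under 6, so under standard equations its limit of 30 is looser than it reads

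*Protocol*

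**What the plan says.** Criterion 17 in Protocol Section 5.2 excludes an estimated GFR below 30 mL/min/1.73 m² "according to the Modification of Diet in Renal Disease study definition". It is the only numeric renal criterion. The introduction to Section 5 rules out eligibility waivers, so sites must apply it as written.

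The population is set in Section 5.1: "Child must be < 6 years at the time of screening" and "Body weight > 8 kg". There is no lower age limit. Section 2.1 explains that the trial accepts children on pumps or "multiple daily injections (MDI) in order to include children below 1 year of age".

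Creatinine is in the central laboratory panel at Visits 1 and 3: "sodium, potassium, calcium, creatinine, total bilirubin, AST, ALT" (Protocol Appendix 2). Body measurements are scheduled at Visit 1 (Protocol Table 1-1), and the SAP demographic shell (Table 14.1.5) carries the footnote "Height, weight and BMI obtained at Screening visit".

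The documents do not write out the MDRD equation, state the ages for which it is meant, offer a pediatric method, or say why MDRD was chosen.

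**The concern.** In its usual form, MDRD uses creatinine, age and sex, with no term for body size, and age enters with a negative power. A small child has little muscle and so a low creatinine, and a young age raises the result further. Both push the estimate up. A fixed limit of 30 on that scale may therefore correspond to a much lower value on a scale that accounts for body size. By contrast, the liver criterion just above it (criterion 16) is a multiple of the upper limit of normal, so it follows whatever reference range applies to the child.

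What is at stake is whether a stated safety limit operates near its stated value. A child passed in this way would be recorded as meeting criterion 17 and would not appear in the SAP listing of unmet eligibility criteria (Listing 16.2.2.3). That child would be one of about four in a dose group.

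**Working it through.** The documents contain no eGFR result to reproduce. The check compares two equations at the limit, and **both equations and all heights are assumptions from outside the documents**.

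**Inputs from the documents:** limit 30 mL/min/1.73 m² by MDRD (Section 5.2); age below 6 with no lower limit (Section 5.1); infants below 1 year foreseen (Section 2.1).

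**Assumed inputs** (creatinine SCr in mg/dL, height in cm):
- MDRD = c × SCr^−1.154 × age^−0.203 (× 0.742 if female), with c = 175 or 186.
- Height-based estimate = k × height / SCr, with k = 0.413 or 0.55.
- Heights: 70 cm at 0.75 years, 75 at 1, 86 at 2, 95 at 3, 102 at 4, 109 at 5 and 115 at 5.9.

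**Step 1: what MDRD reads when the height-based estimate is exactly 30.** Example: a girl aged 2, c = 175, k = 0.413.
- SCr = 0.413 × 86 / 30 = 1.18.
- MDRD = 175 × 1.184^−1.154 × 2^−0.203 × 0.742 = 175 × 0.823 × 0.869 × 0.742 ≈ 93.
- Ratio = 93 / 30 ≈ 3.1.

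**Step 2: what the height-based estimate is when MDRD is exactly 30.** Same girl:
- SCr = (175 × 0.869 × 0.742 / 30)^(1/1.154) ≈ 3.15.
- Height-based estimate = 0.413 × 86 / 3.15 ≈ 11.3.
- For her, the limit of 30 acts like a limit of about 11.

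**Results** (ranges cover both sexes and both constants; the effective limit is the height-based value at which MDRD reaches 30):

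| Age (years) | k | MDRD when height-based = 30 | Ratio | Effective limit |
|---|---|---|---|---|
| 0.75 | 0.413 | 144–206 | 4.8–6.9 | 6–8 |
| 2 | 0.413 | 93–133 | 3.1–4.4 | 8–11 |
| 4 | 0.413 | 66–95 | 2.2–3.2 | 11–15 |
| 5.9 | 0.413 | 53–76 | 1.8–2.5 | 13–18 |
| 0.75 | 0.55 | 103–148 | 3.4–4.9 | 7.5–10 |
| 2 | 0.55 | 67–96 | 2.2–3.2 | 11–15 |
| 4 | 0.55 | 48–68 | 1.6–2.3 | 15–20 |
| 5.9 | 0.55 | 38–55 | 1.3–1.8 | 18–24 |

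The direction is the same in every case: MDRD reads above 30 wherever the height-based estimate is 30. Across the grid the ratio runs from 1.3 to 6.9. The effective limit runs from about 6 to 18 with k = 0.413 and from about 7.5 to 24 with k = 0.55.

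**The case against.** **The size rests on outside equations.** This stands. The documents supply no equation, heights or creatinine values, so the result is a range under stated assumptions. The choice of k alone moves the effective limit near age 6 from 13–18 to 18–24.

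**A reader might infer that the criterion cannot exclude the children it is aimed at.** The figures do not support that. Children with the most severe impairment, below the effective limit, are still excluded. Those missed lie between that limit and 30.

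**A reader might infer a several-fold overestimate at all ages.** That fits the youngest: 3.1 to 6.9 times at ages 0.75 and 2 with k = 0.413. It does not fit near age 6, where the ratio is 1.3 to 2.5 over both values of k.

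**Other safeguards exist.** Criteria 18 (electrolytes), 20 (recent illness) and 21 (any condition jeopardizing safety) could exclude such a child. Medical history, physical examination and biochemistry are also reviewed at screening. This stands in part. A child with true GFR below 30 could pass criterion 17, but the documents do not show that the child would be dosed. These routes rely on judgment, however, and a reassuring eGFR value may inform that judgment.

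**A reader might infer distorted PK results.** The documents do not say that dasiglucagon clearance depends on renal function, and they give no expected number of renally impaired children among the eight. Individual PK parameters are listed (SAP Section 12.4), so an atypical profile would be visible. No planned summary uses eGFR, though, and no covariate adjustment or subgroup analysis is planned (SAP Sections 10.3 and 10.6).

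**Conclusion.** The point holds as a mismatch between a binding eligibility rule and the population to which it applies. Criterion 17 fixes one equation, without justification, for children who are all under 6. Under every combination of assumptions tested, the stated 30 is less strict than it reads: least so near age 6 with k = 0.55 (about 18–24) and most so in infants with k = 0.413 (about 6–8).

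The direction is firm within the assumed forms of the equations; the size is conditional on them. Affected children are probably rare in a trial of eight, and a PK effect is possible but not shown. Neither the primary endpoint analysis nor the sample-size reasoning uses renal function. The correction is worth making because this is a non-waivable safety criterion and the data needed are already collected.

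**What to change.** In criterion 17, replace the reference to MDRD with a named estimating method suited to children under 6, and write out the formula. A height-based creatinine equation is one example. The sponsor should confirm that the chosen method is usable in infants below 1 year, since the trial foresees them. This review changes only the estimating method and proposes no renal threshold.

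Screening already yields creatinine and height, so no extra blood, procedure or visit is needed. The cost is one phrase in a protocol amendment and one formula in the eCRF or at the central laboratory. If the amendment counts as substantial under Protocol Section 10.1.7, authority approval and a favorable ethics opinion are needed before it takes effect. It could be combined with any other planned amendment.
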